APPROVED BY SALUS IRB: 07 MAY 2024

TITLE: Comparative Study of the DMM and Conventional Toric Marker

PROTOCOL NO: IIT# 92162521

AMENDMENT NO: Version 1.0

IRB: Salus IRB
[name]
[name]

SPONSOR: [name] '[name]

INVESTIGATOR: [name] MD
[name]
[name]
United States

**STUDY-RELATED
[contact] (During business hours)
[contact] (24-Hour line)

1. Executive Summary

NEED

There is currently a paucity of data comparing ARGOS combined with the Digital Marker Microscope and other Conventional Marking Modalities for Toric IOL alignment during cataract surgery.

STUDY OBJECTIVE

To evaluate the postoperative refractive accuracy of the common toric Intraoperative marking method of Toric CAM and Mendez marking when compared to ARGOS combined with the Digital Marker Microscope (DMM)/Vision Suite.

STUDY HYPOTHESIS

The DMM linked to Argos preoperative measurements with limbal registration determines the angle for toric IOL alignment intraoperatively more accurately than the manual Mendez marker.

SUPPORTS CLINICAL MESSAGE

The use of ARGOS with intraoperative image guidance improves the toric alignment error significantly and allows for more % of eyes within 0.5D residual CYL (20% more eyes) as compared to manual marking.

STUDY DESIGN

Sample size	35 eyes
Endpoints	
Primary: Difference in intraoperative axis marks with Mendez marker, in degrees and direction, when compared to the DMM as viewed in the intraoperative heads-up display
 
Secondary: % of eyes less than 0.25, 0.5, 0.75, 1.00 and 1.25 D of residual refractive cylinder (CYL) in each group at 1 month postoperatively

Design:	Single-site, head to head, prospective, interventional (all eyes will be planned/implanted using ARGOS with image guidance axis; and the manual marker results will be back calculated utilizing IOL position and post-operative refraction)
DURATION/FOLLOW-UP:	Preoperative to 1 month postoperative

This study will be registered with clinicaltrials.gov. The study will be conducted in compliance with the protocol, GCP, and applicable regulatory requirements.

2. Study Background

Toric IOLs offer patients with corneal astigmatism, increased spectacle independence after cataract surgery. Toric marking aims at improving the accuracy of incision location and IOL alignment. Conventional markers rely on a reference mark tied to gravitational alignment and the accuracy in manual marking methods is affected by head position, errors on marking and smearing of ink. Digital marking methods aim to reduce intraoperative IOL misalignment using images captured in the sitting position which are used as overlay for IOL alignment intraoperatively¹. The DMM linked to ARGOS preoperative measurements with limbal registration determines the exact angle for toric IOL alignment intraoperatively.

The purpose of this study is to compare the outcome of toric IOL implantation guided by manual or digital marking techniques. The intrinsic difference in the toric axis alignment may lead to a significant difference in the marked alignment axis intraoperatively resulting in superior refractive outcomes and less residual astigmatism using intraoperative alignment from the ARGOS Vision planner and DMM.

3. Study Design

- A single site, interventional study comparing the ARGOS/ DMM axis to the Mendez toric marker paired with the toriCAM smart phone app.
- There will be 35 eyes total that meet the inclusion criteria. Patient's refraction will be evaluated 4 weeks after cataract surgery with a monofocal toric IOL (Clareon Toric).
- Intraoperative difference in toric marks will be recorded in degrees and direction of marking difference (clockwise and counterclockwise).
- Post operative refraction will be obtained at 4 weeks after surgery using standard Snellen acuity chart and phoropter. IOL position will be verified with slit lamp photography aligned with preoperative Argos toric imaging to ensure that IOL position is NOT a source of refractive error.
- We will perform back calculation of theoretical refraction, as if the IOL was positioned at Mendez marking axis rather than the Argos axis. This will be calculated using the IOL position and post operative refraction with Astigmatismfix.com calculator or equivalent calculator

4. Study Inclusion and Exclusion Criteria

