4.1 Inclusion Criteria

Subjects are eligible for the study if they meet the following criteria:

- Subjects willing and able to participate in this study.
- Subjects that have signed a consent to participate in the study.
- Subjects that are 50-80 years of age that have had uncomplicated femto-second assisted cataract surgery
- Subjects will have been implanted with the toric Alcon Clareon Toric monofocal IOL
- Subjects with IOLs implanted based on digital marking performed using ARGOS DMM
- Subjects will have BCDVA of LogMar 0.20 (20/32) or better in both eyes
- Subjects able to perform a post-op refraction.

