4.2 Exclusion Criteria

If any of the following exclusion criteria are applicable to the subject, the subject should not be included in the study:

- History of amblyopia, macular disease, glaucoma, corneal disease, prior corneal surgery, or diabetes
- IOL final position greater than 2 degrees from intended axis.
- Ocular comorbidity that might hamper post operative visual acuity
- Previous ocular or refractive surgery
- Expected post-op VA worse than 20/25 (Snellen)
- Irregular corneal astigmatism and keratoconus
- Difficulties comprehending written or spoken English language
- Patients that are unable to fixate due to physical or intellectual disability (e.g. Down's Syndrome, Parkinson's Disease)
- Severe/uncontrolled Ocular surface disease/Dry Eye Disease
- Intraoperative complications during procedure

5. Study Procedures

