5.1 Preoperative

At the preoperative exam, subjects will undergo all routine, usual standard-of-care procedures, including a medical history, demographics, ARGOS biometry, and a slit-lamp and dilated fundus examination. Subjects will then be consented for the study, and a review of inclusion and exclusion criteria will be done prior to the surgery.

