5.2 Operative (Day of Surgery)

All subjects will undergo femto-second assisted cataract surgery with implantation of the Clareon monofocal toric IOL.

The toriCAM smartphone app will be used to mark the horizontal axis as a reference preoperatively in a sitting position. The target axis of the IOL, as calculated by the Argos, will be marked intraoperatively with a Mendez marker based on the horizontal reference marker from the Toric Cam.

After phacoemulsification, the Digital Marker Microscope (DMM) will be used to determine the target axis by using an image overlay

The difference in the final marked IOL axis and the DMM axis will be measured using the DMM degree overlay intraoperatively. The difference in degrees and the direction will be recorded.

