5.3 Postoperative Visits

Subjects will undergo all routine, usual standard-of-care postoperative procedures and follow up appointments.

In addition, 4 weeks following cataract surgery, the final position of the IOL will be confirmed using a slit lamp photograph compared to the ORIGINAL Argos reference image. The surgeon will confirm that the IOL is within 2 degrees of the final intended axis as calculated by the Alcon Vision Planner.

Then the postoperative subjective refraction shall be measured by Snellen and Phoropter method and the theoretical refraction shall be back calculated using the double vector method to arrive with the refraction that would have been obtained by the Mendez marking

method. This will be calculated using the IOL position and post operative refraction with Astigmatismfix.com calculator or equivalent calculation.

6. Statistical Analysis

A summary of the data will be prepared for all measurements. For variables measured on a continuous scale, these summaries will include the sample size, as well as the mean, standard deviation, median, minimum, and maximum. For variables measured on a categorical scale, summaries will provide the number and percentage of eyes in each category. These summaries will be provided for all eyes completing the study.

The statistical analyses will be performed using R, version 4.2.2 or higher. Any statistical tests of hypotheses will employ a level of significance of alpha=0.05.

The primary endpoint will be compared using the paired t-Test. Secondary endpoints will be compared using McNemar's test. Analysis will follow a step down approach:

- Difference in intraoperative axis marks with Mendez marker, in degrees and direction, when compared to the DMM viewed in the intraoperative HUD
- % of eyes less than 0.5D CYL in each group
- % of eyes less than 0.25D CYL in each group
- % of eyes less than 0.75D CYL in each group
- % of eyes less than 1.0D CYL in each group
- % of eyes less than 1.25D CYL in each group

7. Sample Size Justification

Based on the primary endpoint, the study would require a sample size of 21 pairs (to achieve a power of 80% and a level of significance of 5% (two sided), for detecting a mean of the differences of 4.4 between pairs, assuming the standard deviation of the differences to be 6.5.¹

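### The plan counts and tests eyes without a clear one-eye-per-subject rule; if fellow eyes enter with correlated marking differences, the primary t-test does not hold its 5% level

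*Combined protocol and SAP*

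**What the plan says.** **Unit of count and analysis.** The Executive Summary and section 7 give the sample size as 35 eyes, and section 3 says "There will be 35 eyes total that meet the inclusion criteria". Section 6 describes the data by eye: "These summaries will be provided for all eyes completing the study". It assigns a paired t-test to the primary endpoint and McNemar's test to the residual-cylinder thresholds, at a 5% level. No number of subjects appears anywhere.

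**Primary variable.** Section 3 records a signed quantity: "Intraoperative difference in toric marks will be recorded in degrees and direction of marking difference (clockwise and counterclockwise". Section 6 repeats degrees and direction but does not define the number that enters the t-test.

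**Text bearing on a second eye.**
- Section 4.2 is worded by subject ("If any of the following exclusion criteria are applicable to the subject, the subject should not be included in the study") and lists "Previous ocular or refractive surgery", with no mention of study eye or fellow eye.
- Section 4.1 requires that subjects have already had uncomplicated femtosecond-assisted cataract surgery. It also sets an acuity limit: "Subjects will have BCDVA of LogMar 0.20 (20/32) or better in both eyes". It does not say how many of those eyes are study eyes.
- Section 5.1 says "a review of inclusion and exclusion criteria will be done prior to the surgery".
- Section 5.2 is written as one operation and one lens per subject: "All subjects will undergo femto-second assisted cataract surgery with implantation of the Clareon monofocal toric IOL".

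There is no rule for choosing a study eye, and no clustered or mixed-model analysis.

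**The concern.** The pairing in both tests is Mendez against DMM within the same eye. It does nothing about two eyes of one person, which the tests treat as independent. The correlation of 0.80 in section 7 belongs to the comparison of the two methods' percentages and is not a fellow-eye correlation.

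A shared error is plausible on the protocol's own account. Section 2 names head position as a source of manual marking error, and a habitual head tilt while seated could rotate the reference mark the same way in both eyes. That would make the signed differences positively correlated, the standard error too small, and the p-value and interval for the primary too optimistic. A mirror-image error would make the correlation negative and the test conservative. In either case the stated 5% is not the level actually used.

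**Working it through.** **Inputs from the documents.** 35 eyes planned and 30 before the dropout allowance (section 7); mean difference 4.4, SD of differences 6.5, two-sided 5%, 80% power, 21 pairs (section 7).

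**Assumptions, not in the documents.** The number of bilateral subjects *b*; the fellow-eye correlation *ρ* of the signed differences; normal differences; a test of the signed difference against zero.

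**Step 1: the plan's own figure.** Noncentral-t power for a paired t-test at 4.4/6.5 is 79.7% with 19 pairs, 81.9% with 20 and 83.9% with 21. The stated 21 is reproduced to within one pair.

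**Step 2: design effect.** For *n* eyes, of which 2*b* come from bilateral subjects:

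deff = 1 + 2*bρ*/*n*; effective eyes = *n*/deff.

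- *n* = 35, *b* = 3, *ρ* = 0.5: 1 + 3/35 = 1.09; effective eyes 32.2.
- *n* = 35, *b* = 8, *ρ* = 0.5: 1 + 8/35 = 1.23; effective eyes 28.5.
- *n* = 35, *b* = 17, *ρ* = 0.5: 1 + 17/35 = 1.49; effective eyes 23.6.
- *n* = 30, *b* = 15, *ρ* = 0.5: 1 + 15/30 = 1.50; effective eyes 20.0.

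**Step 3: type I error of the planned t-test.** Simulated under a zero mean with bivariate normal fellow eyes and at least 200,000 replicates per cell; repeat runs differ by about 0.1 to 0.2 percentage points. For 35 eyes:

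| Bilateral subjects | *ρ* = −0.3 | *ρ* = 0.1 | *ρ* = 0.3 | *ρ* = 0.5 |
|---|---|---|---|---|
| 0 | 5.0% | 5.0% | 5.0% | 5.0% |
| 3 | 4.4% | 5.1% | 5.6% | 5.9% |
| 8 | 3.5% | 5.5% | 6.6% | 7.7% |
| 17 | 2.1% | 6.1% | 8.4% | 10.9% |

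Hand check of the last cell: 2 × [1 − Φ(1.96/√1.486)] = 2 × [1 − Φ(1.608)] = 10.8%.

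**Step 4: a subject-clustered primary test.** Use a cluster-robust variance with factor *G*/(*G* − 1) and a t reference on *G* − 1 degrees of freedom, where *G* is the number of subjects. For *ρ* from −0.3 to 0.5, its simulated level is 4.9% to 5.4% with 35 eyes (0, 3, 8 or 17 bilateral) and with 30 eyes (3 or 15 bilateral). With no bilateral subjects it is algebraically the planned t-test.

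**Step 5: power at 4.4/6.5 with that test.** It is 97% with 35 eyes and none bilateral, and 87% with 35 eyes, 17 bilateral and *ρ* = 0.5. The worst case is 30 eyes, 15 bilateral and *ρ* = 0.5. There the SD of a subject mean is 6.5 × √(1.5/2) = 5.63, and 15 subject means give 80%.

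**Step 6: interval width against the planned t-test, 35 eyes.**
- *b* = 8, *ρ* = 0.3 (27 subjects): √1.137 × 2.056/2.032 = 1.08.
- *b* = 17, *ρ* = 0.5 (18 subjects): √1.486 × 2.110/2.032 = 1.27.

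**Step 7: McNemar's test.** The plan does not say which form is meant. Under the null, with 35 eyes, 17 bilateral, fellow-eye correlation 0.3 to 0.5 and assumed discordance of 10% to 40%, simulated type I error is 6.3% to 10.5% for the uncorrected test and 1.0% to 7.0% for the exact test.

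**The case against.** The strongest reply is that the text already makes bilateral entry unlikely. The exclusions apply to the subject, one of them is earlier ocular surgery, and eligibility is reviewed before the operation. On that reading, a subject whose first eye was done earlier fails the review for the second. The procedures are also written as one operation and one lens per subject. This stands as far as likelihood goes, and it is why 17 bilateral subjects should be read as an extreme.

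It does not amount to a one-eye rule. The exclusion does not mention the fellow eye. Read literally at subject level, it also conflicts with section 4.1, which requires cataract surgery to have taken place, so some unwritten limit of eye or time must be intended. A subject consented for both eyes before the first operation could pass the review.

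A second reply also stands in part. The documents give no fellow-eye correlation, its sign is unknown, and eyes marked on separate days may share little error. Near zero the effect is small: at 0.1 it is 6.1% even in the extreme case.

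**Conclusion.** The concern holds in conditional form. The plan does not clearly prevent two eyes of one subject from entering, and its eye-level tests have no provision for that. If fellow eyes enter with correlated signed differences, the primary t-test misses its 5% level: by under one percentage point with 3 bilateral subjects, by up to about 2.7 points with 8, and by up to about 6 points in the unlikely case of 17, all at correlations of 0.1 to 0.5. With a negative correlation it is conservative, and with no bilateral subjects nothing changes. The result rests on the assumed bilateral count and correlation, and on a signed test against zero.

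Three stronger readings do not follow:
- *That the 5% level will be exceeded.* The documents show neither bilateral entry nor a positive correlation.
- *That the primary loses its planned power.* Twenty effective eyes still give about 82%, and the clustered test keeps about 80% in the worst case examined.
- *That a false positive on the primary does further damage by opening the secondary tests.* In a fixed step-down order that false positive is already the familywise error, and later tests add nothing to it.

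This is a minor-to-moderate point.

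**What to change.** First, state whether the exclusion for earlier ocular surgery covers the fellow eye, and reconcile it with the section 4.1 requirement for completed cataract surgery. Then choose one option.

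1. **One study eye per subject**, with a selection rule fixed in advance (for example, the first eye operated on). The planned tests and the 35 eyes stay as they are. This costs one eligibility sentence. If the site had meant to enroll both eyes, it needs 35 subjects instead of 35 − 8 = 27 or 35 − 17 = 18, so accrual is slower.
2. **Both eyes may enter, with subject as the cluster.** Use a cluster-robust test with small-sample correction, or a mixed model, for the primary, and a clustered McNemar test or GEE for the thresholds. Report subjects as well as eyes. This costs a few lines of R, and an interval about 8% to 27% wider with 8 to 17 bilateral subjects at correlation 0.3 to 0.5. If no subject turns out to be bilateral, the cluster-robust primary result is identical to the planned one.

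Under either option, define the analyzed primary variable, including its sign convention for right and left eyes, since the direction of the effect depends on it.

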4.1 Inclusion Criteria

Subjects are eligible for the study if they meet the following criteria:

- Subjects willing and able to participate in this study.
- Subjects that have signed a consent to participate in the study.
- Subjects that are 50-80 years of age that have had uncomplicated femto-second assisted cataract surgery
- Subjects will have been implanted with the toric Alcon Clareon Toric monofocal IOL
- Subjects with IOLs implanted based on digital marking performed using ARGOS DMM
- Subjects will have BCDVA of LogMar 0.20 (20/32) or better in both eyes
- Subjects able to perform a post-op refraction.

4.2 Exclusion Criteria

If any of the following exclusion criteria are applicable to the subject, the subject should not be included in the study:

- History of amblyopia, macular disease, glaucoma, corneal disease, prior corneal surgery, or diabetes
- IOL final position greater than 2 degrees from intended axis.
- Ocular comorbidity that might hamper post operative visual acuity
- Previous ocular or refractive surgery
- Expected post-op VA worse than 20/25 (Snellen)
- Irregular corneal astigmatism and keratoconus
- Difficulties comprehending written or spoken English language
- Patients that are unable to fixate due to physical or intellectual disability (e.g. Down's Syndrome, Parkinson's Disease)
- Severe/uncontrolled Ocular surface disease/Dry Eye Disease
- Intraoperative complications during procedure

5. Study Procedures

5.1 Preoperative

At the preoperative exam, subjects will undergo all routine, usual standard-of-care procedures, including a medical history, demographics, ARGOS biometry, and a slit-lamp and dilated fundus examination. Subjects will then be consented for the study, and a review of inclusion and exclusion criteria will be done prior to the surgery.

5.2 Operative (Day of Surgery)

All subjects will undergo femto-second assisted cataract surgery with implantation of the Clareon monofocal toric IOL.

The toriCAM smartphone app will be used to mark the horizontal axis as a reference preoperatively in a sitting position. The target axis of the IOL, as calculated by the Argos, will be marked intraoperatively with a Mendez marker based on the horizontal reference marker from the Toric Cam.

After phacoemulsification, the Digital Marker Microscope (DMM) will be used to determine the target axis by using an image overlay

The difference in the final marked IOL axis and the DMM axis will be measured using the DMM degree overlay intraoperatively. The difference in degrees and the direction will be recorded.

5.3 Postoperative Visits

Subjects will undergo all routine, usual standard-of-care postoperative procedures and follow up appointments.

In addition, 4 weeks following cataract surgery, the final position of the IOL will be confirmed using a slit lamp photograph compared to the ORIGINAL Argos reference image. The surgeon will confirm that the IOL is within 2 degrees of the final intended axis as calculated by the Alcon Vision Planner.

Then the postoperative subjective refraction shall be measured by Snellen and Phoropter method and the theoretical refraction shall be back calculated using the double vector method to arrive with the refraction that would have been obtained by the Mendez marking

method. This will be calculated using the IOL position and post operative refraction with Astigmatismfix.com calculator or equivalent calculation.

6. Statistical Analysis

A summary of the data will be prepared for all measurements. For variables measured on a continuous scale, these summaries will include the sample size, as well as the mean, standard deviation, median, minimum, and maximum. For variables measured on a categorical scale, summaries will provide the number and percentage of eyes in each category. These summaries will be provided for all eyes completing the study.

The statistical analyses will be performed using R, version 4.2.2 or higher. Any statistical tests of hypotheses will employ a level of significance of alpha=0.05.

The primary endpoint will be compared using the paired t-Test. Secondary endpoints will be compared using McNemar's test. Analysis will follow a step down approach:

- Difference in intraoperative axis marks with Mendez marker, in degrees and direction, when compared to the DMM viewed in the intraoperative HUD
- % of eyes less than 0.5D CYL in each group
- % of eyes less than 0.25D CYL in each group
- % of eyes less than 0.75D CYL in each group
- % of eyes less than 1.0D CYL in each group
- % of eyes less than 1.25D CYL in each group

7. Sample Size Justification

Based on the primary endpoint, the study would require a sample size of 21 pairs (to achieve a power of 80% and a level of significance of 5% (two sided), for detecting a mean of the differences of 4.4 between pairs, assuming the standard deviation of the differences to be 6.5.¹

However, in order to achieve a sample size that allows for statistical analysis of the secondary endpoints, we estimate the sample size required for detecting a difference of 0.20 between the percentage of with postoperative residual astigmatism 0.5 D or less (85% compared to 65%), power of 85%, correlation between paired observations 0.80, and a two-sided significance of 5% is 30.²

To account for dropout, the sample size will be increased to 35 eyes.

References

1. Lipsky L, et al. Comparison of toric intraocular lens alignment error with different toric markers. *J Cataract Refract Surg.* 2019; 45:1597–1601.

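### The primary axis difference is recorded in surgery, but the plan's only named population and its 2-degree criterion leave eyes out because of later events

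*Combined protocol and SAP*

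**What the plan says.** **When the primary endpoint is measured.** Section 1 names the Mendez-DMM axis difference as the primary endpoint. Section 5.2 places it in the operating room: "The difference in the final marked IOL axis and the DMM axis will be measured using the DMM degree overlay intraoperatively". It adds: "The difference in degrees and the direction will be recorded".

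**Who is reported.** Section 6 opens with "A summary of the data will be prepared for all measurements" and closes the same paragraph with "These summaries will be provided for all eyes completing the study". Completion is not defined, but Section 1 gives the study's duration as "Preoperative to 1 month postoperative". Section 6 then assigns a paired t-test to the primary endpoint and McNemar's test to the secondary endpoints, and names no population for either.

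**Who is removed later.** Section 4.2 lists "IOL final position greater than 2 degrees from intended axis" among the criteria under which "the subject should not be included in the study". Section 5.3 sets the time of that check: "4 weeks following cataract surgery, the final position of the IOL will be confirmed using a slit lamp photograph". Section 4.1 also requires that the subject can undergo a post-operative refraction. Section 3 explains why lens position is verified: so that it does not contribute to refractive error.

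**Numbers planned.** Section 7 asks for 21 pairs for the primary endpoint and 30 for the secondary, raised to 35 eyes for dropout.

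**The concern.** An eye has a complete primary measurement once surgery is over. Read together, Sections 4.2 and 6 can remove that eye because a visit was missed, because no refraction was obtained, or because the lens was found off axis 4 weeks later. None of these is part of the endpoint. The reason given for the 2-degree check applies to the refractive endpoints, where the theoretical Mendez refraction is back-calculated from lens position. It gives no ground for discarding an axis comparison made in surgery.

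Two things are at stake. One is precision, which is lost without any gain. The other is selection on an event after the measurement. All lenses are placed on the DMM axis, so a DMM registration error would enter both the recorded difference and the lens position later checked against the Argos image. Dropping off-axis eyes could then preferentially drop eyes with large DMM error.

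**Working it through.** **Inputs.** Mean difference 4.4, SD of differences 6.5, two-sided alpha 0.05, 80% power, 21 pairs, 30 eyes for the secondary endpoint, 35 enrolled (all Section 7). The figure of 25 eyes is an assumption, to show the effect if the 2-degree rule removes more eyes than the dropout allowance covers. The plan states no rule for replacing eyes, so none is assumed.

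**1. The plan's own figure.** For a paired t-test, power comes from the noncentral t with n − 1 degrees of freedom and noncentrality (4.4/6.5)·√n. This gives 79.7% at n = 19, 81.9% at n = 20 and 83.9% at n = 21. The smallest adequate n is 20, so the stated 21 is reproduced to within one pair.

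**2. The dropout allowance.** 35 − 30 = 5 eyes, and 5/35 = 14.3%. The plan makes no separate allowance for eyes failing the 2-degree check.

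**3. Precision and power by number of eyes analysed.** Half-width of the 95% interval = t(0.975, n − 1) × 6.5/√n.

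- n = 35: 2.032 × 1.099 = 2.23 degrees; power 97.3%
- n = 30: 2.045 × 1.187 = 2.43 degrees; power 94.8%
- n = 25: 2.064 × 1.300 = 2.68 degrees; power 90.1%

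Relative to 35 eyes, the interval is about 9% wider with 30 (2.43/2.23) and about 20% wider with 25 (2.68/2.23).

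**4. How much selection could matter.** The documents give no DMM registration error, so this step rests on assumptions. Let the DMM error be normal with mean 0 and SD s, and the placement error normal with mean 0 and SD s/2. An eye is kept if the absolute sum of the two is at most 2 degrees. The overall SD of the Mendez-DMM difference is held at 6.5. The sum has variance 1.25s², so the variance of the difference among kept eyes is 6.5² − 0.8·s²·(1 − v), where v is the factor by which the cut-off shrinks the variance of the sum.

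- 30 of 35 kept: s = 1.22, v = 0.534. Variance 42.25 − 0.56 = 41.69, so SD 6.46 (down 0.7%).
- 25 of 35 kept: s = 1.68, v = 0.326. Variance 42.25 − 1.52 = 40.73, so SD 6.38 (down 1.8%).

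The errors have mean zero and the cut-off is symmetric, so the expected mean difference is unchanged in both cases.

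**The case against.** **The completer sentence governs descriptive summaries, not the test.** This is literally correct. A reader might infer that the plan expressly restricts the t-test to completers, but the text does not say so. What remains is that the summaries cover all measurements, so the reported mean and SD of the primary endpoint are affected on any reading. For the test, completers are the only population on offer.

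**Removal of off-axis eyes comes from eligibility, not from Section 6.** This is also correct, and it affects the remedy. A new sentence in Section 6 alone would conflict with Sections 4.1 and 4.2, which would still exclude those eyes.

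**The loss does not affect the planned conclusion.** This stands as far as power goes. The plan needs 21 pairs, and power is 90.1% even with 25 eyes. The case rests on data discarded without need.

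**The selection argument is speculative.** This largely stands. A reader might infer that dropping off-axis eyes biases the primary result or materially understates the spread of disagreement. The documents contain nothing to show that loss depends on the axis difference. Under symmetric errors the mean is unbiased, and the SD falls by no more than about 2% when 25 to 30 eyes are kept. To bring the SD down to about 6.0, the same model needs a DMM error SD of 3 degrees. It then keeps only about 45% of eyes (about 16 of 35), which is far from anything the plan anticipates.

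**Conclusion.** The point holds, at modest size. Followed as written, the plan omits valid intraoperative measurements from the primary summaries, and by fair inference from the paired t-test, because of events up to 4 weeks later. The cost is a 95% half-width of 2.43 degrees with 30 eyes, or 2.68 with an assumed 25, instead of 2.23 with 35. These figures rest on the plan's SD of 6.5, on all 35 eyes having an intraoperative measurement, and on no replacement of lost eyes.

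The documents do not support a claim that the trial is underpowered for its primary endpoint, or that the primary estimate is biased. Selection through DMM-guided lens position is a possibility that the plan leaves open and could easily close. The change is worth making because it recovers precision and removes that possibility with data already collected.

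**What to change.** Three linked edits:

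- **Section 6:** define the primary analysis set as every eye with a recorded intraoperative Mendez-DMM difference, regardless of 4-week attendance or final lens position. State that both the summaries and the paired t-test for the primary endpoint use this set.
- **Sections 4.1 and 4.2:** restate the 2-degree condition and the post-operative refraction condition as requirements for the refractive (secondary) analysis set only, so that they no longer remove an eye from the study.
- **Reporting:** give the number of eyes left out of the refractive set, with reasons and their primary values, so that readers can judge whether those eyes differ.

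No extra data or visits are needed. The cost is a text amendment to three sections, and primary and secondary analyses with different denominators, which the report should state.
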